To evaluate the activity of single-agent nanatinostat, the first 20 patients enrolled with PTCL will be randomized 1:1 to either nanatinostat monotherapy (20 mg PO once daily on Days 1 to 4 per week in Cohort 3a) or nanatinostat plus valganciclovir (in Cohort 3b). Following a disease response assessment at 6 weeks, patients in Cohort 3a with a CR or PR will continue nanatinostat monotherapy. Those in Cohort 3a with stable disease at 6 weeks or disease progression at any time (confirmed by CT or MRI) will have the option to cross over to combination therapy for the remainder of the study. Patients must complete the End of Monotherapy Disease assessment and

qualify (labs, no sign of CNS disease progression and Eastern Cooperative Oncology Group [ECOG]) prior to beginning Cycle 1 Day 1 of the nanatinostat plus valganciclovir combination therapy.

Cohort 7 will be closed to enrollment when all other cohorts are closed, regardless of the number of patients recruited at that time and will not be subject to the decision criteria of the Simon's 2-stage design.

It is thus estimated that up to 486 patients in Cohorts 1 to 6 may be enrolled for combination therapy, of which approximately 60 would be enrolled in Stage 1, 66 would be enrolled in Stage 2, and up to 360 would be enrolled in the post-Stage 2 expansion cohorts. Additional patients (n=10) with PTCL will be enrolled in Cohort 3a for nanatinostat monotherapy, and patients with lymphoma subtypes other than those assigned to Cohorts 1, 3, 4, 5, and 6 may be enrolled into Cohort 7 (with the exception of France; see above).

If 10 patients of a given lymphoma subtype are enrolled into Cohort 7, then the Simon's decision criteria will be applied to determine whether or not to add patients in Stage 2 for that subtype. If none of the subtypes represented in Cohort 7 enrolls at least 10 patients, efficacy data collected on those patients will be listed, but not summarized by group. All patients will be summarized for safety, regardless of decision to discontinue enrollment into any cohort.

[figure not shown]
Patients enrolled in Cohorts 1 to 7 (with the exception of Cohort 3a), and patients crossed over from Cohort 3a will receive intermittent dosing of nanatinostat and continuous valganciclovir in 28-day cycles as follows:

- a. Nanatinostat 20 mg orally once daily on Days 1 to 4 per week (ie, 4 days on, 3 days off)

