#### 3.1.2. Treatment Period

Patient eligibility will be confirmed once all screening procedures are completed.

Enrolled patients will receive treatment until disease progression (per Investigator assessment), unacceptable toxicity, withdrawal of consent, Investigator's discretion, death, initiation of new antineoplastic therapy, discontinuation from the study for any reason, or study termination by the Sponsor. Patients receiving nanatinostat monotherapy who have disease progression will be offered the option to receive combination therapy with valganciclovir. All antineoplastic therapies given after the last dose of study drug (and time to next therapy) will be recorded in the electronic case report form (eCRF) (unless the patient withdraws consent or is lost to follow-up). Patients will be followed for survival regardless of treatment discontinuation reason (except if consent is withdrawn or patient is lost to follow-up).

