# **5.6.2.** Treatment Assignment (Including Randomization)

Patients will be enrolled into each cohort based on their primary lymphoma diagnosis to receive the combination nanatinostat plus valganciclovir with exception of Cohort 3a.

The first 20 patients enrolled with PTCL in Cohort 3 will be randomized 1:1 to either Cohort 3a (nanatinostat monotherapy) or Cohort 3b (nanatinostat plus valganciclovir). Randomization will occur at the time of drug dispensation for Cycle 1 Day 1. Following a disease response

assessment at 6 weeks, patients in Cohort 3a with a CR or PR will continue nanatinostat monotherapy. Those in Cohort 3a with stable disease at 6 weeks or disease progression at any time will be offered the option to cross over to combination therapy for the remainder of the study, provided they qualify per hematology, chemistry, no sign of CNS disease progression, and ECOG parameters (see Section 4.1.1).

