If a Cohort 3a patient has stable disease at the Day 43 visit (or progressive disease at any time), the patient will be offered the option to cross over to combination nanatinostat/valganciclovir therapy and follow the 28-day treatment cycles as described above. Patients must complete the End of Monotherapy Disease assessment and qualify (labs, no sign of central nervous system [CNS] disease progression, Eastern Cooperative Oncology Group [ECOG]) prior to beginning Cycle 1 Day 1 of the nanatinostat/valganciclovir combination therapy. If a patient has a response (complete or partial response) to nanatinostat monotherapy at the Day 43 visit, the patient will continue monotherapy treatment.

For patients enrolled in Cohorts 1 to 7 (with the exception of Cohort 3a prior to potential crossover to combination therapy), disease response assessments will be made every 8 weeks until 24 weeks, and then every 12 weeks for the remainder of the study, according to the revised response criteria for malignant lymphoma based on the International Working Group (IWG) guidelines (Cheson 2007). A scan to confirm an unconfirmed partial response (PR) or unconfirmed complete response (CR) \geq 4 weeks later may also be performed. Responses will be assessed by both the Investigator and an Independent Review Committee (IRC).

The safety and tolerability of study drug treatments will be evaluated by means of adverse event (AE) reports (incidence, causality, and severity), ECOG performance status, physical examinations, 12-lead electrocardiograms (ECGs), and laboratory safety evaluations. Laboratory abnormalities and AE severity will be graded according to National Cancer Institute (NCI) *Common Terminology Criteria for Adverse Events* (CTCAE), version 5.0.

Upon discontinuation of the protocol-specified treatments, patients will enter the Follow-up period. All patients will be followed for AEs for 28 days after the last dose of study drug (permanent discontinuation) and complete the Safety Follow-up visit as described in Section 7.2.5 of the clinical study protocol, except if the patient is lost to follow-up or withdraws consent. The PK parameters of nanatinostat and its metabolites

and ganciclovir (primary active hydrolytic product of valganciclovir) will be evaluated for patients enrolled in Stage 1 and sparse sampling will be collected during the Stage 2 part of the study at selected sites.

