4.5.4 Secondary Endpoint Analysis Methods

The ORR per investigator assessment, CRR per IRC review, and CRR per investigator assessment will be summarized using the same methods as described for the primary efficacy endpoint.

Time to response, DOR, DOCR, TTNLT, TTP, PFS, and OS will be summarized in days using Kaplan-Meier (KM) methodology. The number of patients who experienced the event of interest and the number of patients censored will be presented; as will KM product limit estimates of the median with associated CIs (where estimable) using Greenwood's formula. The range for all patients, as well as those who experience the event of interest will also be summarized. Kaplan-Meier estimates of the survival distribution function for DOR, PFS, and OS over time will be generated and all derived efficacy measures will also be provided in a separate listing.

For Cohort 3a patients who crossover to receive combination therapy, DOR and DOCR will only be applicable after crossover given the requirement that patients only cross over from monotherapy to combination therapy after stable disease at the Day 43 visit (or progressive disease at any time).

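### The SAP rule that Cohort 3a crossover patients have DOR only after crossover drops the monotherapy DOR of a responder who later progresses and crosses over

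*SAP*

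**What the plan says.** SAP 4.5.4 (Secondary Endpoint Analysis Methods) sets the rule for Cohort 3a patients who cross over: "DOR and DOCR will only be applicable after crossover given the requirement that patients only cross over from monotherapy to combination therapy". The requirement it then cites is a Day 43 finding of stable disease, or progression whenever it occurs. The same sentence thus gives the rule and its reason.

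The pathway around it is described as follows.

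- **Responders stay on monotherapy.** SAP 3.1: "If a patient has a response (complete or partial response) to nanatinostat monotherapy at the Day 43 visit, the patient will continue monotherapy treatment". Protocol 3.1 agrees: "patients in Cohort 3a with a CR or PR will continue nanatinostat monotherapy".
- **They are followed for progression.** Protocol Table 6, footnote 4, scans patients who continue monotherapy at Weeks 14, 22 and 34, then every 12 weeks until relapse or progression.
- **Progression opens crossover, with no time limit, in several places.** Protocol 5.6.2: "Those in Cohort 3a with stable disease at 6 weeks or disease progression at any time will be offered the option to cross over". Protocol 3.1.2: "Patients receiving nanatinostat monotherapy who have disease progression will be offered the option to receive combination therapy with valganciclovir". The Study Design part of the Protocol Synopsis, Protocol 3.1, SAP 3.1 and SAP 3.3.2 are to the same effect. None excepts earlier responders.
- **Other places are narrower.** The treatment part of the Protocol Synopsis and Table 6, footnote 1, mention only stable or progressive disease at Day 43, or progression before it. Protocol 7.2.1 mentions only Day 43.
- **DOR itself.** SAP 3.4.1.2 runs DOR from first CR or PR to progression, death or last adequate assessment, and derives it per IRC and per investigator. Table 3 in SAP 4.5.6.2 counts progression as an event.

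**The concern.** The SAP infers that nobody who crosses over can have had a monotherapy response. Stable disease at Day 43 supports that inference, as does progression without any earlier response. Progression at any time does not, because it includes a 6-week responder who relapses months later.

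That patient has a response date and a progression date on monotherapy, which is a complete DOR, yet the rule makes it not applicable. The loss is selective: it falls on responders who crossed over, chiefly after progressing, while those still in response remain. Cohort 3a was added because the protocol (Section 3) reports no clinical data for nanatinostat alone in lymphoma. Protocol 9.1 asks for the two randomized PTCL sub-cohorts to be summarized separately. An inflated monotherapy DOR would blur that description.

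**Working it through.** The plan gives no figure to reproduce, so the check traces the rule and then illustrates its effect.

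**1. Routes into crossover**

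| Route | Monotherapy response first? | Effect of SAP 4.5.4 |
|---|---|---|
| Stable disease at Day 43 (same assessor) | No | Nothing lost |
| Progression with no earlier response | No | Nothing lost |
| CR or PR at 6 weeks, later progression, crossover | Yes | Monotherapy DOR dropped |
| Stable disease per investigator, PR per IRC at Day 43, crossover | Yes, per IRC | IRC monotherapy DOR dropped |

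The third route follows from the sections that set no time limit. The fourth arises because Protocol 7.3.1.2 uses the investigator's reading for management and the IRC's for endpoints. It exists even if crossover is confined to Day 43.

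**2. Does another section restore the lost DOR?** SAP 4.5 lists a display of patients randomized to monotherapy, but says nothing about DOR that overrides the specific rule. SAP 4.6.2 splits Cohort 3a by period for adverse events only.

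**3. Direction in a small example (assumed data).** Three responders have DOR of 4 months (progression), 8 months (progression) and 10+ months (censored). The median is the first time at which the Kaplan-Meier estimate S is 0.5 or less.

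- All kept: S(4) = 1 − 1/3 = 2/3; S(8) = 2/3 × (1 − 1/2) = 1/3. Median 8.
- Both progressors cross over: one censored patient, 0 events, median not reached.
- Only the first crosses over: S(8) = 1 − 1/2 = 1/2. Median still 8.
- Only the second crosses over: S(4) = 1 − 1/2 = 1/2. Median 4.

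One very small sample can therefore move either way; the upward bias is a statement about expectation.

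**4. Large-sample illustration.** Assumptions: exponential DOR, follow-up uniform from 6 to 36 months, 400,000 simulated responders per setting, and a stated share of progressing responders crossing over, unrelated to when they progressed. Kaplan-Meier median in months under the rule as written:

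| True median | 25% cross | 50% cross | 75% cross | 100% cross |
|---|---|---|---|---|
| 4 | 4.1 | 4.4 | 5.3 | not reached |
| 6 | 6.4 | 7.3 | 10.2 | not reached |
| 12 | 13.9 | 18.0 | 33.4 | not reached |

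Keeping every monotherapy DOR recovers the true median in each row.

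**5. Could it arise with 10 patients?** P(at least one monotherapy responder) = 1 − (1 − p)^10, which is 0.65, 0.89 and 0.99 for an assumed ORR p of 10%, 20% and 35%. An affected patient must also progress and cross over. If a share c of responders does so, the chance is 1 − (1 − pc)^10. With c assumed to be 0.5:

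- p = 10%: 1 − 0.95^10 = 0.40
- p = 20%: 1 − 0.90^10 = 0.65
- p = 35%: 1 − 0.825^10 = 0.85

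**The case against.** The strongest objection is that the protocol does not speak with one voice. If the treatment part of the Synopsis, Table 6 footnote 1 and Protocol 7.2.1 governed, a responder who progresses after Day 43 would have no crossover route, and the SAP's inference would hold for that patient. This stands as a reason to reconcile the text. It does not remove the point, because the SAP sentence itself refers to progression at any time, and the disagreement between assessors at Day 43 would remain.

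Second, the sentence could be read as governing only the crossover display in SAP 4.5, leaving the randomized-to-monotherapy display to carry every monotherapy DOR. That would be a sensible intention, but the SAP does not write it for DOR.

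Third, a reader might infer that monotherapy DOR would be left with almost no events. The documents do not support that. Crossover is optional and depends on laboratory values, ECOG status and absence of CNS progression. Responders who progress and do not switch, or who die on monotherapy, stay in as events. The not-reached medians are the extreme in which every progressor crosses over. For IRC-assessed DOR, moreover, a progression called only by the investigator is not an event, so what is dropped there is not always an event.

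Fourth, the consequence is small. Monotherapy DOR feeds no decision rule, analyses are descriptive with no formal comparison of cohorts, and the sentence leaves ORR, CRR, PFS and TTP untouched. The swimmer plot would still show each patient's course, though it would not correct the Kaplan-Meier summary.

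**Conclusion.** The point holds in limited form. The reason given in SAP 4.5.4 does not support its rule, and the rule as written removes the monotherapy DOR of a responder who progresses and then crosses over. The expected effect is an upward bias in monotherapy DOR, and in DOCR for complete responders. Its size rests on the share of progressing responders who cross over, which is unknown, so the figures above are illustrations only.

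The scope is at most 10 patients and a descriptive secondary endpoint. A reader might infer that the combination result is also distorted; it is not, since the primary combination ORR does not use this rule. Nor can it be said that both documents consistently allow crossover at any time. The main route depends on the sections that set no time limit, which are the more numerous and include the SAP sentence itself.

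**What to change.** Replace the SAP 4.5.4 sentence with a by-period rule:

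- **Monotherapy period.** Every Cohort 3a monotherapy responder has a monotherapy DOR (and DOCR if CR) running to progression or death, otherwise censored under Table 3, whether or not the patient later crosses over.
- **After crossover.** A separate DOR and DOCR start at a new response, measured against the crossover baseline scan already defined in SAP 4.5.3.
- **Both assessors.** Apply the rule separately per IRC and per investigator. Table 3 has no row for crossover before progression by that assessor, so state the handling, for example censoring at the last assessment before the first combination dose. An IRC responder who switches straight after Day 43 would then add almost no follow-up, but would be counted.

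Also reconcile the treatment part of the Synopsis, Table 6 footnote 1 and Protocol 7.2.1 with the Synopsis Study Design, Protocol 3.1, 3.1.2 and 5.6.2, and SAP 3.1 and 3.3.2, on when crossover is open. Which wording should govern is for the sponsor to settle.

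The analysis cost is one amended SAP sentence and a two-period derivation, with no new data collection. The SAP already uses such a split for Cohort 3a adverse events. If no responder ever crosses over, the results are unchanged.

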4.5.5 Additional Efficacy Endpoint Analysis Methods

Each patient's EBV viral load will be plotted over time by cohort and displayed on logarithmic scales.

Additional exploratory endpoints will be described in a separate analysis plan.

4.5.6 Statistical/Analytical Issues

4.5.6.1 Adjustments for Covariates

There are no planned applications of covariate adjustments; all statistical results are descriptive in nature.

4.5.6.2 Handling of Dropouts or Missing Data

Overall response is based on those patients with available data (baseline and post-baseline response assessment). Non-evaluable patients are considered non-responders and will be included in the denominator. Progression-free survival and DOR will be right-censored for patients who meet one of the following conditions: 1) non-protocol systemic anti-cancer treatment started before documentation of disease progression or death, 2) death or disease progression after more than one missed disease assessment visit, or 3) alive and does not have documentation of disease progression before a data analysis cutoff date. These conventions are based on the FDA Guidance for Industry, Clinical Trial Endpoints for the Approval of Cancer Drugs and Biologics (2018) and Clinical Trial Endpoints for the Approval of Non-Small Cell Lung Cancer Drugs and Biologics (2015). The analyses of PFS and DOR will be right-censored according to the conventions described in the table below.

Table 3 Censoring Conventions for Progression-Free Survival, Time to Progression, and Duration of Response

Situation	Date of Progression for Censoring	Outcome
No baseline tumor assessments	Randomization (if applicable) or enrollment	Censored
New anti-cancer therapy started before documentation of PD or death	Date of last disease assessment prior to start of new anti-cancer therapy	Censored*
Death or PD immediately after more than one consecutively missed disease assessment visit	Date of last disease assessment visit without documentation of PD that is before the first missed visit	Censored
Alive and without PD documentation	Date of last disease assessment	Censored
Death or PD between planned disease assessments	Date of death or first disease assessment showing PD, whichever occurs first	Progressed

Situation	Date of Progression for Censoring	Outcome
Death before first disease assessment	Date of death	Progressed

*PFS, TTP, DOR will additionally be analyzed without censoring for hematopoietic stem cell transplant

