## 9.3. Definition of Analysis Populations

The following 4 populations will be used in the analysis:

- 1. **Intent-to-Treat (ITT) population:** All patients who are enrolled into the trial, regardless of whether they received study treatment or not.
  - The ITT population will be used for the primary efficacy analysis. Patients will be analyzed according to their disease/cohort. If a patient has no post-baseline tumor assessment for efficacy, they will be counted as a treatment failure in this population analysis.
- 2. **Modified ITT (mITT) population:** All enrolled patients who have received at least one dose of study medication, met all eligibility criteria, and have at least one post-baseline tumor assessment for efficacy.
  - The efficacy analysis will also be performed on the mITT population as supportive evidence and/or sensitivity analyses. Patients will be analyzed according to their cohort and overall.
- 3. **Safety population:** All patients who have received at least one dose of study medication will be summarized for safety based on cohort and overall.
- 4. **PK population:** All patients with PK assessments.

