4.1.1 Reporting Conventions

The Simon 2-stage and post-Stage 2 expansion parts of the study will be analyzed separately. For safety analyses only, all patients who receive combination therapy over the course of the study will also be analyzed separately.

Tables and figures will be summarized by cohort within each part. A more detailed description for how these data will be presented for each type of analysis (e.g., safety, efficacy, etc.) is provided in subsequent sections herein. In general, all data collected and any derived data will be presented in patient data listings for all enrolled patients. Listings will be ordered by phase, site, cohort, patient number, and assessment or event date. The cohort presented in listings will be based on the planned assignment, unless otherwise noted.

In general, continuous variables will be summarized to indicate the study population sample size (N), number of patients with available data (n), mean, SD, median, first (Q1) and third (Q3) quartiles, minimum, and maximum values. Categorical variables will be summarized by the population size (N), number of patients with available data (n), number of patients in each category, and the percentage of patients in each category. Unless otherwise noted, the denominator to determine the percentage of patients in each category will be based on the number of patients with available data. Select ordinal data may be summarized using both descriptive statistics and counts and percentages of patients in each category, as appropriate.

Non-zero percentages will be rounded to one decimal place. Rounding conventions for presentation of summary statistics will be based on the precision of the variable of summarization, as it is collected in its rawest form (i.e., on the electronic case report form [eCRF] or as provided within an external file) and are outlined as follows:

- The mean and median will be rounded to one more decimal place than the precision of the variable of summarization;
- Measures of variability (e.g., SD, SE) will be rounded to two more decimal places than the precision of the variable of summarization; and
- Minimum and maximum values will be presented using the same precision as the variable of summarization.

Other statistics (e.g., CIs) will be presented using the same general rules outlined above or assessed for the most appropriate presentation based on the underlying data.

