4.2 Analysis Sets

The analysis sets are defined as follows:

- Intent-to-Treat Analysis Set: All patients who are enrolled into the trial, regardless of whether they received study treatment or not.
- Modified Intent-to-Treat Analysis Set: All enrolled patients who have received
 at least one dose of study medication with a confirmed diagnosis of lymphoma
 subtype by central pathology review. The primary efficacy analysis will be
 performed in the Modified Intent-to-Treat Analysis Set per FDA guidance and
 historical precedent.
- Efficacy-Evaluable Analysis Set: All enrolled patients who have received at least one dose of study medication, met all eligibility criteria, and have at least one adequate (radiographic) post-baseline tumor assessment.
- Safety Analysis Set: Patients who have received at least one dose of study medication will be summarized for safety by cohort and over all patients combined.

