4.7 Determination of Sample Size

This multinational, multicenter study will employ a Simon's optimal 2-stage design to allow termination of enrollment into cohorts where treatment appears futile (Simon 1989). The decision to transition from Stage 1 to Stage 2 is dependent on the assumption of ORR: ORR \leq 10% (poor response); ORR \geq 35% (good response). The sample size estimation uses 1-sided alpha = 0.05 and targets statistical power = 85%.

Using the Simon's 2-stage design approach, the null hypothesis that the true response rate is 10% will be tested against a one-sided alternative. In the first stage, up to 10 patients will be accrued in each cohort. If there are 1 or fewer responses, the cohort will

be discontinued. If the cohort fails to enroll any patients within 1 year from the enrollment of the first patient, the cohort will be considered for termination of enrollment. Otherwise, if at least 2 patients in a cohort respond, additional patients will be accrued for a total of 21 in the cohort. The null hypothesis that the true response rate is 10% will be rejected in each cohort where 5 or more responses are observed in 21 patients. This design yields a type I error rate of 0.0440 and power of 86.2% within each cohort where the true response rate is 35%.

If 10 patients of a given lymphoma subtype are enrolled into Cohort 7, then the Simon's decision criteria will be applied to determine whether or not to add patients in Stage 2 for that subtype. If none of the subtypes represented in Cohort 7 enrolls at least 10 patients, efficacy data collected on those patients will be listed, but not summarized by group. All patients will be summarized for safety, regardless of the decision to discontinue enrollment into any cohort.

If at the end of Stage 2 there are at least 7 responders observed in the initial 21 patients in any cohort (ORR \geq 33.3%), enrollment will be expanded to include up to 120 additional patients in that cohort (N=141), with an interim analysis in that cohort to be performed as described in Section 4.5.6.3. Simon's Stage 2 estimate was ORR=33.3% for the PTCL cohort. Using Clopper-Pearson Exact confidence interval approach, the sample size for a 95% CI that would exclude 25% if the ORR was 33.3% was N=120. Using ORR=35%, the minimum sample size is estimated to be N=85.

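### SAP 4.5.6.2 is inconsistent on the denominator of the primary ORR; read literally, its first sentence would drop dosed but unscanned mITT patients

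*SAP*

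**What the plan says.** SAP 4.5.6.2 opens with two sentences on response:

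- First sentence: "Overall response is based on those patients with available data (baseline and post-baseline response assessment").
- Second sentence: "Non-evaluable patients are considered non-responders and will be included in the denominator".

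The SAP does not define 'non-evaluable'. SAP 4.5.3, which gives the primary analysis, asks for the number and percentage with CR or PR by cohort with a Clopper-Pearson 95% CI and names no denominator. SAP 4.1.1 sets a general default: "Unless otherwise noted, the denominator to determine the percentage of patients in each category will be based on the number of patients with available data".

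The analysis sets differ between the documents:

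- Protocol 9.3, ITT (primary in the protocol): "If a patient has no post-baseline tumor assessment for efficacy, they will be counted as a treatment failure in this population analysis".
- Protocol 9.3, mITT (supportive): dosed patients who "met all eligibility criteria, and have at least one post-baseline tumor assessment for efficacy".
- SAP 4.2, mITT (primary in the SAP): "at least one dose of study medication with a confirmed diagnosis of lymphoma" subtype by central pathology review. There is no scan requirement.
- SAP 4.2, Efficacy-Evaluable (supportive): dosed, eligible patients who "have at least one adequate (radiographic) post-baseline tumor assessment".

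SAP 4.8 declares the move away from ITT as the primary set but states no rule for unscanned patients. On ITT, SAP 4.5.1 and 4.8 make efficacy summaries optional, to be repeated if they differ meaningfully from mITT. SAP 4.5.6.6 says ITT will be used as a sensitivity analysis.

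**The concern.** The two sentences give different answers for a patient who was dosed, has a centrally confirmed subtype, and has no post-baseline scan. Such a patient is in the SAP's mITT set. The first sentence leaves the patient out of the response analysis. The second keeps the patient in as a non-responder if 'non-evaluable' covers patients with no scan, but does not reach the patient if the term means only scanned and rated not evaluable.

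These patients are foreseeable. Table 3, in the same section, has rows for no baseline tumor assessment and for death before the first disease assessment. The first scheduled scan is at 8 weeks (6 weeks in Cohort 3a). SAP 4.5.6.3 also lets patients who permanently stopped treatment count towards the 40 at the interim analysis.

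A patient with no post-baseline scan cannot be a documented responder, so removing such patients can only raise the ORR and its limits. The primary mITT result would also come close to the Efficacy-Evaluable result, which is meant to be a separate supportive check. The CRR is affected in the same way, because SAP 4.5.4 uses the primary endpoint's methods for it.

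**Working it through.** **1. Which denominator is intended?** The protocol's mITT required a post-baseline assessment. The SAP took that requirement out, made mITT primary, and placed the requirement in the Efficacy-Evaluable set. Applying it again through 4.5.6.2 would undo that change. The protocol's treatment-failure rule for unscanned ITT patients points the same way. The full mITT denominator is therefore the likelier intent, but no sentence in the SAP says so.

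**2. Method.** For x responders among n, the exact (Clopper-Pearson) limits are: lower = the 0.025 quantile of Beta(x, n − x + 1); upper = the 0.975 quantile of Beta(x + 1, n − x).

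**3. Reproducing the SAP's figures.**

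- 26/40 = 65.0%: 48.3% to 79.4% (SAP 4.5.6.3: 48%, 79%).
- 21/40 = 52.5%: 36.1% to 68.5% (SAP Table 4: 36%, 68%).
- 25/50 = 50.0%: 35.5% to 64.5% (Table 4: 36%, 64%).
- 29/60 = 48.3%: 35.2% to 61.6% (Table 4, observed rate 48%: 35%, 61%).
- 40/120 = 33.3%: lower limit 24.99%. SAP 4.7 says "the sample size for a 95% CI that would exclude 25% if the ORR was 33.3% was N=120", which holds to rounding. This count is therefore not used as an example of a crossing.

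**4. How many dropped patients would matter?** Take the largest responder count whose lower limit clearly falls below the benchmark with the full denominator. Hold x fixed and remove unscanned non-responders until the limit passes the benchmark.

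| Setting | Benchmark | Full denominator | After dropping | Dropped |
|---|---|---|---|---|
| Expansion, 120 | 25% | 39/120: 24.2% | 39/116: 25.1% | 4 (4/120 = 3.3%) |
| Second line, 40 | 35% | 20/40: 33.8% | 20/38: 35.8% | 2 (2/40 = 5.0%) |
| Second line, 50 | 35% | 24/50: 33.7% | 24/48: 35.2% | 2 (2/50 = 4.0%) |
| Second line, 60 | 35% | 28/60: 33.7% | 28/57: 35.6% | 3 (3/60 = 5.0%) |

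One patient fewer dropped is not enough in three of these: 39/117 gives 24.9%, 20/39 gives 34.8% and 28/58 gives 34.95%.

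**5. One responder lower in the second-line rows.**

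- 19/40: 31.5%; 19/36: 35.5% (4 dropped, 10.0%).
- 23/50: 31.8%; 23/45: 35.8% (5 dropped, 10.0%).
- 27/60: 32.1%; 27/55: 35.4% (5 dropped, 8.3%).

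The number needed rises quickly, so the effect is confined to counts close to the benchmark.

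**6. Count rules.** Two of 10 to continue, 5 of 21 to reject the 10% null, 7 of 21 to expand, and 26 responses among 40 at the interim are all numbers of responses. Removing non-responders changes none of them.

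**The case against.** **The second sentence already settles it.** Only that sentence uses the word denominator. The first can be read as saying what a response determination rests on, and the second as saying what happens to patients who lack one. An unscanned patient plainly fails the Efficacy-Evaluable definition, so 'non-evaluable' naturally covers that patient. This is the most natural reading and it stands as the probable intent. It means the first sentence cannot be called simply wrong; the pair is inconsistent as worded. It does not remove the problem, because the term is undefined and the first sentence restricts response to patients with both assessments.

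**The 4.1.1 default gives way.** It applies unless otherwise noted, and the second sentence is arguably such a note. That holds only if the second sentence covers unscanned patients.

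**The outputs would show it.** SAP 4.1.1 presents both the population size and the number with data, SAP 4.3.1 gives the number in each analysis set, and SAP 4.5.1 lists excluded patients with reasons. A careful reader could recompute the ORR. This limits the risk of a hidden bias but does not fix the prespecified estimate.

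**Stronger readings the documents do not support.**

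- A reader might infer that dropping patients could trigger the interim claim of overwhelming efficacy, since 24/36 = 66.7% exceeds 65%. The rule requires at least 26 responses among 40 patients, so 24 fails under either denominator.
- A reader might infer that the Simon error rates are compromised. SAP 4.5.6.5 says no hypothesis testing is planned, while SAP 4.7 does state a rejection rule at 5 of 21. That rule is a count and is unaffected.
- A reader might take the earlier VT3996-201 study (64 enrolled, 50 evaluable) as an unscanned rate. Protocol 1.2.4 does not define evaluable there, so the figure cannot be used that way.

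**The ITT question is separate.** That is correct, and it is treated below as secondary.

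**Conclusion.** The inconsistency is real and should be fixed; confidence is medium. The probable intent is the full mITT denominator, but the text also permits a reading that removes dosed, unscanned patients from the primary ORR, and that reading can bias the estimate only upwards.

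The consequence is for interpretation. Expansion enrolment continues whatever the interim shows, and crossing 25% or 35% triggers no stated action. Even so, the SAP justifies its sample sizes by whether the 95% CI excludes a benchmark rate. At the borderline counts shown, dropping 2 to 4 patients (3.3% to 5.0%) reverses that statement. Away from such counts nothing crosses.

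The calculation assumes that every dropped patient is a non-responder and that the number of responders is fixed. It shows what could happen, not how likely it is: the documents give no rate of missing post-baseline scans and no probability of a borderline count.

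Separately, SAP 4.5.1 and 4.8 do not agree with 4.5.6.6 on whether ITT results will be shown. Because a meaningful difference is not defined, the choice would be made after the data are seen.

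**What to change.** Replace the first sentence of SAP 4.5.6.2 with: 'For ORR and CRR the denominator is all patients in the analysis set; patients with no baseline or no adequate post-baseline assessment, or with an IRC response of not evaluable, are counted as non-responders.' Add that this applies instead of the available-data default in SAP 4.1.1.

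As a secondary change, reconcile SAP 4.5.1 and 4.8 with 4.5.6.6 by committing to present the ITT ORR whatever the observed difference from mITT.

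The cost is a few sentences and one ITT table. The reported ORR may be slightly lower than under a literal reading of the present first sentence.
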